6.7 Early Withdrawal

For subjects who discontinue early from treatment, consolidation, or maintenance, the reason for discontinuation should be provided and the End-of-Treatment visit should be performed. The subject will be entered into Quarterly Follow-up, unless consent is withdrawn, for 12 months after the last dose of investigational product (tabelecleucel and/or pembrolizumab).

For a subject who discontinues early from quarterly follow-up, the reason for discontinuation should be provided and the last Quarterly Follow-up Visit will be considered the end-of-study for the subject.

7 EFFICACY AND SAFETY ASSESSMENTS

7.1 Radiographic Tumor Assessments

Local site study team reading (investigator assessment with site radiology reading) based on RECIST 1.1 and immune (i)RECIST will be used to determine subject eligibility and clinical treatment decisions during the course of the study. RECIST 1.1 will be adapted to account for the unique tumor response characteristics seen with treatment of pembrolizumab to immune iRECIST. Immunotherapeutic agents such as pembrolizumab may produce antitumor effects by potentiating endogenous cancer-specific immune responses. The response patterns seen with such an approach may extend beyond the typical time course of responses seen with cytotoxic agents and can manifest a clinical response after an initial increase in tumor burden or even the appearance of new lesions. Standard RECIST 1.1 may not provide an accurate response assessment of immunotherapeutic agents such as pembrolizumab. Therefore, RECIST 1.1 will be used with the adaptations described in Section 15.5.

Disease progression will be based on radiographic measurements according RECIST 1.1 and iRECIST. For clinically stable subjects, if imaging shows progressive disease (unconfirmed

progressive disease), it is at the discretion of the investigator to keep a subject on treatment with investigational product or to stop treatment with investigational product until repeat imaging is performed 4-6 weeks later in order to confirm progressive disease since T-cell infiltration of a tumor can cause the appearance of radiographic progression in subjects who subsequently respond [49]. Subjects who are deemed clinically unstable are not required to have repeat imaging for confirmation prior to stopping treatment. This decision will be based on clinical judgment of a subject's overall clinical condition, including performance status, clinical symptoms, and laboratory data, and in consultation with the sponsor's medical monitor.

When feasible, subjects should not be discontinued until progression is confirmed. This allowance to continue treatment despite initial radiologic progression takes into account the observation that some subjects can have a transient tumor flare in the first few months after the start of immunotherapy, but with subsequent disease response.

7.1.1 *Rationale for Endpoints Related to RECIST*

The central radiology vendor will perform retrospective IRR of scans in support of primary and secondary study objectives. OS will be included as it is a standard assessment of clinical benefit in subjects with NPC. ORR and the duration of response by RECIST 1.1 criteria as assessed by IRR will serve as additional measures of efficacy.

RECIST 1.1 will be used to determine the dates of progression as this methodology is accepted by regulatory authorities. Since the treatment assignment is unblinded, images read by a central imaging vendor blinded to treatment assignment (ie, IRR) can minimize bias in the response assessments. In addition, final determination of radiologic progression will be based on the central imaging vendor assessment of progression, rather than site study team assessment.

7.1.2 *Tumor Imaging and Assessment of Disease*

The process for image collection and transmission to the central imaging vendor for IRR can be found in the Radiology Manual. Tumor imaging may be acquired by CT or MRI. For the abdomen and pelvis, contrast-enhanced MRI may be used when CT with iodinated contrast is contraindicated, or when mandated by local practice. The same imaging technique regarding modality, ideally the same scanner, and the use of contrast should be used in a subject throughout the study to optimize the reproducibility of the assessment of existing and new tumor burden and improve the accuracy of the assessment of response or progression based on imaging. Note: for the purposes of assessing tumor imaging, the term "investigator" refers to the investigator at the study site and/or the radiological reviewer located at the site or at an offsite facility.

Imaging should include the chest, abdomen, pelvis, as well as the head and neck. Brain imaging is required for all subjects at screening. MRI is preferred; however, CT imaging will be acceptable, if MRI is medically contraindicated.

Expedited confirmation of measurable disease based on RECIST 1.1 by IRR at screening will be used to determine subject eligibility. Confirmation by the central imaging vendor that the subject's imaging shows at least 1 lesion that is appropriate for selection as a target lesion per RECIST 1.1 is required prior to subject treatment.

All scheduled images for all study subjects from the study sites will be submitted to the central imaging vendor for IRR. In addition, images (including via other modalities) that are obtained at an unscheduled time point to determine disease progression, as well as imaging obtained for other reasons, but captures radiologic progression based on investigator assessment, should also be submitted to the central imaging vendor for IRR.

7.1.2.1 *Initial Tumor Imaging*

Initial tumor imaging at screening must be performed prior to the date of the first dose of investigational product. The study site study team must review screening images to confirm the subject has measurable disease per RECIST 1.1. The screening images must be submitted to the IRR vendor for retrospective confirmation of measurable disease per RECIST 1.1 for eligibility prior to the date of the first dose of investigational product. Tumor imaging performed as part of routine clinical management is acceptable for use as screening tumor imaging if it is of diagnostic quality and can be assessed by the central imaging vendor.

If brain imaging is performed to document the stability of existing metastases, MRI should be used if possible. If MRI is medically contraindicated, CT with contrast is an acceptable alternative.

7.1.2.2 *Tumor Imaging During the Study*

The first on study imaging assessment should be performed after Treatment Cycle 2 Day 15 between Days 16 to 21, and thereafter, after each treatment and consolidation cycle Day 15 between Days 16 to 21. Subsequent tumor imaging should be performed during the Maintenance Phase on Day 77 (\pm 2 days) of each cycle, at the end-of-treatment (30 \pm 5 days after the last dose of investigational product), and during the Quarterly follow-up phase (every 90 \pm 14 days), or more frequently if clinically indicated.

Objective response should be confirmed by a repeat imaging assessment. Tumor imaging to confirm an initial treatment response of PR or CR will occur during the subsequent consolidation cycle.

Per iRECIST (Section 7.1.4), disease progression should be confirmed by the study site 4 to 8 weeks after site-assessed first radiologic evidence of progressive disease in clinically stable subjects. Subjects, who have unconfirmed disease progression may continue on treatment at the discretion of the investigator until progression is confirmed by the site, provided they have met the conditions detailed in Section 7.1.4. Subjects who receive confirmatory imaging do not need to undergo the next scheduled tumor imaging if it is less than 4 weeks later; tumor imaging may resume at the subsequent scheduled imaging time point, if clinically stable. Subjects, who have confirmed disease progression by iRECIST, as assessed by the study site, will discontinue treatment with investigational products. Exceptions are detailed in Section 7.1.4.

7.1.2.3 *End-of-Treatment and Quarterly Follow-up Tumor Imaging*

For subjects who discontinue treatment with investigational products, tumor imaging should be performed at the End-of-Treatment Visit (30 \pm 5 days after the last dose of investigational

product). If previous imaging was obtained within 4 weeks prior to the date of discontinuation, then imaging at treatment discontinuation is not mandatory. For subjects who discontinue both investigational products due to documented disease progression, this is the final required tumor imaging if the investigator elects not to implement iRECIST.

For subjects who discontinue study treatment without documented disease progression, every effort should be made to continue monitoring disease status by tumor imaging using the same imaging schedule used while on treatment until the start of a new anticancer treatment, disease progression, pregnancy, death, withdrawal of consent, or the end of the study, whichever occurs first.

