4.2.1 Inclusion Criteria

A subject will be considered eligible to participate in this study if all of the following inclusion criteria are satisfied:

1. Male or female \geq 12 years of age
2. Incurable, locally recurrent or metastatic NPC (World Health Organization type II/III) in whom the EBV nucleic acid or antigens have been demonstrated in tissue biopsy samples
3. Subjects must have had prior receipt of platinum-containing regimen, *either*:
 - a. For the treatment of recurrent or metastatic disease, *or*
 - b. Experienced progression of disease within 6 months following completion of a platinum-based combination therapy as part of (neo)adjuvant chemotherapy. Note: Patients who had only concurrent chemoradiation therapy without (neo)adjuvant therapy and then recurred/metastasized must have progressed on at least 1 platinum-containing regimen for their recurrent/metastatic disease before study entry.
4. Phase 1B (Cohort 1):
 - a. Checkpoint inhibitor naïve (have never received pembrolizumab or any other anti-PD-1, anti-PD-L1, anti-PD-L2, anti-CD137, anti-OX40 or anti-CTLA-4 antibodies)

OR

- b. Refractory to an anti-PD-1 or anti-PD-L1 monoclonal antibody approved by the local regulatory agency either as monotherapy or in combination with other checkpoint inhibitors or therapies according to their approved label. To be considered refractory to an anti-PD-1 or anti-PD-L1 monoclonal antibody, all of the following criteria must be met:
 - i. Received at least 2 doses of anti-PD-1 or anti-PD-L1 monoclonal antibody at a local regulatory agency-approved dose and schedule.

- ii. Have progressive disease after anti-PD-1 or anti-PD-L1 monoclonal antibody as defined according to RECIST 1.1. The initial evidence of progressive disease is to be confirmed by a second assessment, no less than 4 weeks from the date of the first documented progressive disease, in the absence of rapid clinical progression. (The eligibility determination will be made by the investigator and then the sponsor will collect for retrospective analysis at a central vendor. Once progressive disease is confirmed, the initial date of progressive disease documentation will be considered the date of disease progression).

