15. Pregnancy or breastfeeding; females of childbearing potential must have a negative serum pregnancy test. The serum pregnancy must be confirmed negative within 72 hours of Cycle 1 Day 1 (first dose of investigational product) for the subject to be eligible.
16. Female of childbearing potential or male with a female partner of childbearing potential unwilling to use a highly effective method of contraception (abstinence is acceptable) for the course of the study through 120 days after the last study dose.
17. Inability to comply with study procedures
18. Received chemotherapy or targeted small molecule therapy within 2 weeks of Cycle 1 Day 1. Subjects must have recovered (ie, grade ≤ 1 or at baseline) from AEs due to a previously administered agent. Subjects with grade ≤ 2 neuropathy or grade ≤ 2 alopecia are an exception to this criterion.
19. Received prior radiotherapy within 2 weeks of Cycle 1 Day 1. Subjects must have recovered from all radiation-related toxicities, not require corticosteroids, and not have had radiation pneumonitis. A 1-week washout is permitted for palliative radiation (≤ 2 weeks of radiotherapy) to non-central nervous system (CNS) disease.
20. Antibody/biologic therapy within 4 weeks of Cycle 1 Day 1 or not recovered (ie, grade ≤ 1 or at baseline) from AEs due to agents administered more than 4 weeks earlier
21. Carcinomatous meningitis and/or active CNS metastases, unless metastases are treated and stable and the subject does not require systemic steroids NOTE: Subjects with previously treated brain metastases may participate provided they are stable (without evidence of progression by imaging [using the identical imaging modality for each assessment, either magnetic resonance imaging (MRI) or computed tomography (CT) scan] for at least four weeks prior to the first dose of investigational product and any neurologic symptoms have returned to baseline), have no evidence of new or enlarging

brain metastases, and are not using steroids for at least 7 days prior to first dose of investigational product. This exception does not include carcinomatous meningitis which is excluded regardless of clinical stability.

22. History or current evidence of any condition, therapy, or laboratory abnormality that might confound the results of the study, interfere with the subject's participation for the full duration of the study, or is not in the best interest of the subject to participate, in the opinion of the treating investigator

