6.2 Screening

Within 28 days prior to study enrollment (Cycle 1 Day 1), the following *required* assessments/procedures will be collected or performed after consent is signed, unless otherwise specified:

- Written informed consent by the subject or the subject's legally authorized representative
- Verification that subject meets all inclusion and exclusion criteria
- Complete medical history
- Physical examination
- Height and weight

- Performance status: ECOG for subjects > 16 years of age or Lansky score for subjects 12 to 16 years of age
- AEs considered at least possibly related to study procedure(s)
- Concomitant medications
- Vital signs (body temperature, blood pressure (BP), heart rate (HR), and respiratory rate)
- **CC1**
[REDACTED]
- Radiographic assessments (MRI or CT with contrast) as described in Section [7.1](#)
- **CC1**
[REDACTED]
- Hematology panel: complete blood count (CBC) with platelet count and differential
- Coagulation panel: prothrombin time (PT), activated partial thromboplastin time (aPTT), and international normalized ratio (INR)
- Full chemistry panel: sodium, potassium, chloride, total carbon dioxide, blood urea nitrogen (BUN), creatinine, glucose (fasting), total calcium, albumin, total protein, serum creatinine, total bilirubin (TBIL), ALT, AST, alkaline phosphatase, and tests of thyroid function (thyroid stimulating hormone [TSH], T3, and T4)
- **Cohort 1, checkpoint inhibitor (PD-1/PD-L1) failed subjects only:**
 - Tumor/active site biopsy or archival sample as described in Section [7.2](#) (central laboratory); hematology and coagulation panels must be performed prior to biopsy
 - Initial evidence of progressive disease with confirmation assessment retrospective analysis at a central vendor, refer to inclusion criterion [4.b.ii](#)
- **Cohort 1, checkpoint inhibitor-naïve subjects, and Cohort 2:** Archival tumor block/tumor sections if available (central laboratory)

Within 72 hours prior to Cycle 1 Day 1, the following procedure will be performed:

- Pregnancy test for women of childbearing potential (serum)

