15 APPENDIX

15.1 Schedule of Assessments and Procedures

Evaluation	Inventory Check ^a	Screening ^a	Treatment/Consolidation Cycles with Observation (21-day) ^a				Maintenance Cycles with Observation (84-day) ^a			EOT Visit ^a	Quarterly Follow-up ^a
			Day 1	Day 8	Day 15	Day 21	Day 1	Days 21, 42, 63	Day 77		
Signed informed consent	X	X									
High resolution HLA typing ^b	X										
Eligibility criteria		X									
CMV antibody status	X									X ^c	
Demographics	X										
Medical history		X									
Pregnancy test		X ^d								X ^d	
Physical examination		X	X	X	X		X	X		X	
Height and weight	X ^e	X	X ^e	X ^e	X ^e		X ^e	X ^e		X ^e	
Vital signs ^f		X	X ^g	X ^h	X ^h		X ^g	X ^h		X	
Performance status ⁱ		X								X	
Concomitant medications		X	X	X	X	X	X	X	X	X	
AEs ^j	X ^k	X ^k	X	X	X	X	X	X	X	X	X ^l
Hematology, coagulation and chemistry panels ^m		X ⁿ	X ^o		X ^p		X ^p	X ^o		X ^p	
CCI											
CCI											
CCI											
Tumor/active site biopsy		X ^t		X ^u							

Evaluation	Inventory Check ^a	Screening ^a	Treatment/Consolidation Cycles with Observation (21-day) ^a				Maintenance Cycles with Observation (84-day) ^a			EOT Visit ^a	Quarterly Follow-up ^a
			Day 1	Day 8	Day 15	Day 21	Day 1	Days 21, 42, 63	Day 77		
Radiographic assessments ^v		X ^{w,x}				X ^x			X ^x	X ^x	X ^w
Tabelecleucel dosing ^y			X	X	X		X				
Pembrolizumab dosing ^y			X				X	X			
Survival and disease status											X

Abbreviations: AE: adverse event, ALT: alanine aminotransferase, aPTT: activated partial thromboplastin time, AST: aspartate aminotransferase, BP: blood pressure, BUN: blood urea nitrogen, CBC: complete blood count, CD: cluster of differentiation, CMV: cytomegalovirus, CR: complete response, CT: computed tomography, [CCl] , [CCl] , [CCl] , ECOG: Eastern Cooperative Oncology Group, EOT: End-of-Treatment, [CCl] [CCl] HR: heart rate, HLA: human leukocyte antigen, ICF: informed consent form, INR: international normalized ratio, IV: intravenous(ly), MRI: magnetic resonance imaging, NPC: nasopharyngeal carcinoma, PD-1: programmed cell death protein-1, PD-L1: programmed death-ligand1, PR: partial response, PT: prothrombin time, SAE: serious adverse event, SD: stable disease, TBILI: total bilirubin, TSH: thyroid stimulating hormone.

a) PROCEDURAL NOTES:

Inventory check: within 5 to 10 days prior to screening

Screening: within 28 days prior to enrollment (Cycle 1 Day 1) or Days -28 to -1

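### The baseline scan may predate the last chemotherapy or radiotherapy, so shrinkage from that treatment can be counted as a response to the combination

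*Protocol*

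**What the plan says.** **Scan timing.** Protocol 7.1.2.1 states: "Initial tumor imaging at screening must be performed prior to the date of the first dose of investigational product". Besides this sentence, the only limit is the screening window. Section 6.2 lists the radiographic assessment among procedures done "Within 28 days prior to study enrollment (Cycle 1 Day 1"), and Section 15.1 repeats it: "Screening: within 28 days prior to enrollment (Cycle 1 Day 1) or Days -28 to -1". A scan from ordinary care can serve: "Tumor imaging performed as part of routine clinical management is acceptable for use as screening tumor imaging", provided it is of diagnostic quality and the central vendor can read it.

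**Washout.** Exclusion 18 bars a subject who "Received chemotherapy or targeted small molecule therapy within 2 weeks of Cycle 1 Day 1". Exclusion 19 bars one who "Received prior radiotherapy within 2 weeks of Cycle 1 Day 1", but adds: "A 1-week washout is permitted for palliative radiation" for courses of 2 weeks or less outside the central nervous system. Antibodies, biologics and other investigational products have a 4-week washout (exclusions 20 and 25).

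**Disease status at entry.** Inclusion 3 begins "Subjects must have had prior receipt of platinum-containing regimen". Route 3a needs only that platinum was given for recurrent or metastatic disease. Route 3b needs progression within 6 months of (neo)adjuvant platinum combination therapy. The Note requires subjects who had only concurrent chemoradiation before recurrence to have progressed on a platinum regimen for their recurrent or metastatic disease.

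**SAP.** Section 6.1 takes as baseline the last value on or before the first dose. Sections 8 and 8.1.1 disregard assessments made after a new anti-NPC therapy starts. Neither mentions therapy given between the baseline scan and the first dose. Section 1 records that the study stopped in Phase 1B with 12 subjects, and Section 6.2 plans no efficacy hypothesis.

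**The concern.** RECIST response is measured against the baseline sum of diameters. If that sum is recorded before the last cycle of chemotherapy or before a lesion is irradiated, the comparison with on-study scans mixes the effect of the earlier treatment with that of the combination. In a single-arm study no control group shares the effect, so it goes straight into ORR, which is tested against a fixed 20%.

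The safeguards in the plan do not separate the two effects. Confirmation at 28 days or more uses the same baseline. Central review reads the same images; its screening check asks whether there is a measurable target lesion, not when the scan was taken relative to prior therapy. Inclusion 9 accepts a lesion in a previously irradiated area only if progression has been documented in it, but does not address a lesion irradiated after the scan.

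**Working it through.** **1. Overlap between scan window and washout** (Protocol 6.2, 15.1 and 4.2.2). Overlap = 28 days minus washout.

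| Prior therapy | Washout (days) | Longest possible treatment after the scan (days) |
|---|---|---|
| Chemotherapy, targeted small molecules | 14 | 28 - 14 = 14 |
| Radiotherapy | 14 | 28 - 14 = 14 |
| Palliative radiation outside the central nervous system | 7 | 28 - 7 = 21 |
| Antibodies, biologics, investigational products | 28 | 28 - 28 = 0 |

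A complete 2-week palliative course fits inside the 21 days.

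**2. Interval to the first on-study scan.** Protocol 7.1.2.2 places it on Cycle 2 Days 16 to 21, which is study days 37 to 42, or 36 to 41 days after Day 1. From a Day -28 baseline this is 28 + 36 = 64 to 28 + 41 = 69 days.

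**3. The plan's own test** (Protocol 9.5: N = 36, null 20%, target 45%, one-sided exact 0.025). The smallest r with P(X ≥ r | 36, 0.20) ≤ 0.025 is r = 13. This gives alpha 0.0182 and power 0.893, in agreement with the stated 90%. With r = 12, alpha is 0.0424, which is too large.

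**4. The larger analysis set.** Protocol 9.2 adds checkpoint-inhibitor-naïve Cohort 1 subjects treated at the RP2D. At least 6 of the 12 at a dose level must be refractory, so at most 6 are naïve and N is at most 36 + 6 = 42. The smallest r for N = 42 is 15, with alpha 0.0130.

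**5. Effect of carry-over on the planned test.** The documents give no rate, so c, the share of true non-responders scored as responders through carry-over, is an assumption. At a true ORR of 20% the observed rate is 0.20 + c × (1 - 0.20), and the chance of success is P(X ≥ r) at that rate.

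| Assumed c | Observed rate | N = 36, r = 13 | N = 42, r = 15 |
|---|---|---|---|
| 0 | 0.200 | 1.8% | 1.3% |
| 1% | 0.208 | 2.5% | 1.8% |
| 2% | 0.216 | 3.3% | 2.6% |
| 5% | 0.240 | 7.0% | 6.0% |
| 10% | 0.280 | 18.3% | 17.2% |

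The nominal 2.5% is passed at c just above 1% for N = 36 and at about 2% for N = 42. The table counts carry-over only; it makes no allowance for growth between scan and Day 1.

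**6. Effect on what will be reported.** One misattributed response adds 1/12 = 8.3 points to ORR among all 12 subjects. SAP Section 8 reports the sub-cohorts separately; if 6 subjects are naïve (an assumption, and the maximum under the entry rule), one response adds 1/6 = 16.7 points there.

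**The case against.** Several points on the other side stand.

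- **Platinum Note.** A reader might infer from route 3a that any naïve subject still responding to platinum can enter. The Note rules that out for subjects whose earlier treatment was concurrent chemoradiation alone: they cannot enter while still responding to their only platinum regimen. The opening is limited to other subjects on route 3a.
- **Direction.** A reader might infer that early scans bias ORR upward. Carried-over responses do raise it, but where prior therapy had failed, untreated growth between an early scan and Day 1 makes response harder to reach. The net direction is not certain.
- **Persistence.** If the last chemotherapy was 14 days before Day 1, shrinkage must still be present 14 + 36 = 50 to 14 + 41 = 55 days later, and again at 78 days or more to be confirmed. This makes high carry-over rates less plausible. It does not remove the problem, since both scans use the same baseline, and SAP 8.1.1 does not restate confirmation.
- **Radiation.** Inclusion 9 gives partial protection, so the radiation route is weaker than the chemotherapy route.
- **Concomitant-therapy restriction.** Protocol 5.3.2 restricts chemotherapy and radiation during the study. The exclusions nevertheless permit them until 2 weeks or 1 week before Day 1, and routine-care scans are accepted, so this does not clearly close the gap. The Radiology Manual might add a rule, but it is not among the documents.
- **Termination.** The phase 2 test was not run, and new protocol wording cannot change scans already taken. This confines the present consequence to the descriptive results.

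**Conclusion.** The concern holds as a permitted possibility. The visible text allows up to 14 days of chemotherapy, targeted therapy or radiotherapy, or up to 21 days of palliative radiation, after the baseline scan, and nothing in the protocol or SAP keeps resulting shrinkage out of ORR. It does not extend to antibodies, biologics or investigational products.

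The size is conditional. The error rates rest on an assumed carry-over of 1% to 10% of non-responders and describe the planned phase 2 test only. A reader might infer that the trial's type I error was in fact inflated; the documents do not support this, because they give no carry-over rate and the SAP plans no efficacy test. For the 12 enrolled subjects, the exposure is 8.3 points of ORR per misattributed response overall, and 16.7 points in a naïve sub-cohort of 6 if that is its size. Whether any such response occurred cannot be told from the documents. A cheap correction is worth making.

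**What to change.** **Protocol 6.2 and 7.1.2.1, for the design as planned.** Require the baseline scan to be acquired after the last dose or fraction of prior anticancer therapy and within 28 days of Cycle 1 Day 1. As a backstop, do not allow a lesion irradiated after that scan to be selected as a target lesion. This concerns measurement timing only; no change to the washout periods is suggested.

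**SAP Section 8, which still applies to the 12 enrolled subjects.** List subjects whose baseline scan predates their last prior therapy, with both dates, and report ORR and CBR with and without them. The summary of prior therapy in SAP 7.4 does not provide this, because it does not relate therapy dates to the scan.

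**Cost.** Two sentences in the protocol, and one listing and one sensitivity table in the SAP, provided the scan and prior-therapy dates are available. Sample size, critical value and power do not change. Some scans would have to be timed later and some routine-care scans would no longer qualify. Delayed shrinkage after the last dose would be reduced but not removed, since a scan taken soon after that dose would still meet the rule.
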